The treatment decision will be made by the patient's MS treating physician as part of standard of care for MS patients having an acute exacerbation. After the patient's treating physician has recommended ACTH, the study will be offered to the patient and the consenting process will be initiated, as described in eIRB. If the patient agrees to participate and signs the consent and HIPAA forms, he/she will become a study subject and randomized to one of two treatment groups. The initial stage of the study is for all patients to receive the standard of care course of ACTH and depending on the randomization, a patient may or may not receive additional monthly doses of ACTH. If the patient does not enroll into the study, ACTH will be prescribed as standard of care. Participation in this study will be offered to every eligible patient. Every physician in Judith Jaffe MS Center is an investigator for this study and will be discussing the study with their eligible patients.

The initial course of ACTH (H.P. Acthar®) will be administered as recommended in the package insert, a subcutaneous daily dose of 80-120 units daily for 2-3 weeks. However, as recommended in the package insert, the dosage may be individualized according to the medical condition of each

patient. Therefore, the frequency and dose of the drug may be determined by considering the severity of the disease and the initial response of the patient. The typical dosing for an MS exacerbation is 80units/day for 3-5 days and it is expected that this will be the initial dosing for the majority of the patients.

MS patients enrolled in this study will be randomized into:

Group A: 80units/day ACTH for 3-5 days (The dose could be adjusted based on the individual needs of the patients up to 80-120 units daily for 2-3 weeks.)

Group B: 80units/day ACTH for 3-5 days (The dose could be adjusted based on the individual needs of the patients up to 80-120 units daily for 2-3 weeks.), followed by monthly 80 units/day ACTH for 3 days for 12 months of treatment.

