The Judith Jaffe Multiple Sclerosis Center currently has over 1000 patients in a clinical and MRI database. Patients who have signed consent for the database will have their standard of care MRI scans monitored for new enhancing lesions; this will only have to be repeated if initial scan is not completed at our MS center with our current clinical protocol. All RRMS patients with new enhancing lesions will be considered for the study and approached regarding participation. Patients that are considered candidates and consent for the study, patients will then be randomized (1:1) to receive one course of ACTH followed by monthly pulses vs. receiving only one course of ACTH treatment. All patients will have follow-up MRI's at 3 months, 6 months and 12 months post lesion onset for a total of 3 additional scans. If a patient is identified as having an enhancing lesion from MRI scan not obtained through our database, an additional scan will be obtained through the study and serve as the baseline MRI. All patients will receive the first course of ACTH within 4 weeks of new lesion detection.

3.2: Study endpoints

The primary endpoint of this study will be change in MWF within new enhancing lesions over the course of 12 months. The absolute change in lesion MWF (over our test-retest variability) between baseline and one year MRI's will be calculated and compared between treatment groups.

The main secondary end-point will be longitudinal assessment of MWF (every 3 months) to determine the dynamics of myelin change over 12 months, specifically to determine the timing of remyelination. The advantage of T2 relaxometry is the ability to look at both the contribution of water within myelin bilayers (MWF) but also the water within the intra/extracellular compartment (the intermediate peak within the T2 spectrum). This second peak (extracellular peak) can increase with edema, thus once the extracellular pool stabilizes, we can ensure that any change in myelin water fraction (MWF) is a true reflection of myelination.

We will also explore a measurement called “absolute myelin content”. Through this measurement, we can control for the increased edema associated with a new lesion, thus providing for a more accurate measure of true myelin change.

Additional secondary end points include measurement of the following clinical measurements: EDSS, and the following MRI measurements: change in T2 lesion volume, whole brain volume, and cortical volume.

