Given this is a small pilot study and a chance that simple randomization would course all patients to fall within one treatment group we will randomize patients *in permuted blocks*. This randomization scheme consists of a sequence of blocks such that each block contains a pre-specified number of treatment assignments in random order. The purpose of this is so that the randomization scheme is balanced at the completion of each block. Patients will be randomized after the consent is signed.

3.5 Sample Size:

We are proposing a pilot to study fifteen patients per study arm (for a total of 30 patients, includint ~ 10 screen failures) with new enhancing lesions over a 12 month time period. The longitudinal dynamics of MWF have only been studied in a handful of patients and the effect of any specific steroid treatment has not been studied, thus we are unable to propose a proper calculated sample size. However, from our preliminary longitudinal MWF lesion data, we are able to determine that at least 50% of new enhancing lesions show some signs of remyelination after initial acute treatment (methylprednisolone or ACTH). If we were to perform a sample size based upon an assumption that repeated course of ACTH will show a 25% greater proportion of lesions showing signs of improvement, we would require approximately 53 lesions per arm. In order to achieve that goal, we would have to screen and enroll at least 50 patients per arm. Therefore we are proposing a small pilot study to gain more information regarding the potential benefit of repeated courses of ACTH to allow for a more accurate design of a larger clinical trial. In addition, we will focus our efforts toward patients with more than one lesion in an attempt to reach a goal of at least 25 lesions per arm. We expect that repeated course of ACTH may profoundly affect the remyelination and hope to a much higher proportion of lesions showing repair. Again, we are hopeful that information gained from this pilot study can help to accurately calculate sample sizes for larger clinical trials as well as gain insight into the potential benefit of ACTH on remyelination.

3.6 Clinical visit schedule:

Screening visits: Patients will be screened during standard of care clinical visits for multiple sclerosis. If a patient had MRI within 2 weeks of visit and had new enhancing lesions, the patient will be asked to participate in the study.

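### Section 3.4's permuted blocks, at one centre with no described blinding and treating physicians as recruiters, leave up to a quarter to a half of assignments foreseeable unless block sizes vary and are concealed

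*Protocol*

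**What the plan says.** Protocol section 3.4 chooses permuted blocks over simple randomisation. It says that "each block contains a pre-specified number of treatment assignments in random order" and that the aim is that "the randomization scheme is balanced at the completion of each block". On timing, it says "Patients will be randomized after the consent is signed". It gives no block size, does not say whether the size varies, and does not say who holds the list.

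Section 3.1 sets the ratio and the arms: "patients will then be randomized (1:1) to receive one course of ACTH followed by monthly pulses vs. receiving only one course of ACTH treatment". One arm has a three-day pulse each month for a year and the other has nothing after the initial course. No sham or blinding is described.

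Section 3.1 also has the treating physician recommend ACTH before the study is raised. Every physician at the centre "is an investigator for this study and will be discussing the study with their eligible patients". The stated safeguard against selective recruitment is "Participation in this study will be offered to every eligible patient".

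Section 3.5 gives fifteen patients per arm and 30 in total, worded so that about 10 screen failures may be counted within the 30.

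**The concern.** Forced balance makes the end of a block predictable: once one arm's places are used up, everything left in the block belongs to the other arm. That does no harm if recruiters cannot see past assignments or cannot tell where a block ends. Here the arms look different once monthly pulses begin, there is one centre, and the physicians who treat and follow patients also decide whom to approach.

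A physician who can work out the next arm could, knowingly or not, hold back or bring forward a patient because of severity, lesion number or expected need for more treatment. The arms would then differ at entry in ways that randomisation is meant to prevent. The primary comparison of 12-month MWF change would carry that difference. With 15 or fewer patients per arm, a few such choices could matter.

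**Working it through.** The protocol gives no figure for predictability. Its one calculated design figure, about 53 lesions per arm in section 3.5, does not enter here.

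**Inputs.** Allocation 1:1 (section 3.1). Blocks balanced at completion (section 3.4). Number randomised: 30, or about 20 if the screen failures are counted within the 30 (section 3.5). Block size: not stated, so 2, 4, 6 and 10 are assumptions. It is also assumed that the size is constant and known or inferred, and that recruiters know the earlier assignments in order.

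**Certain assignments.** In a block of 2m, an assignment is certain once one arm's m places are filled. The expected number per block is 2m/(m+1):

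- size 2: 2/2 = 1 of 2, or 50%
- size 4: 4/3 = 1.33 of 4, or 33%
- size 6: 6/4 = 1.5 of 6, or 25%
- size 10: 10/6 = 1.67 of 10, or 17%

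**Best guess.** Guess the arm that is behind, and toss a coin when the arms are level. Expected correct guesses per block are m + (2^(2m)/C(2m,m) − 1)/2:

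- size 2: 1 + (4/2 − 1)/2 = 1.5 of 2, or 75%
- size 4: 2 + (16/6 − 1)/2 = 2.83 of 4, or 71%
- size 6: 3 + (64/20 − 1)/2 = 4.1 of 6, or 68%
- size 10: 5 + (1024/252 − 1)/2 = 6.53 of 10, or 65%

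Unrestricted randomisation gives 50%. This guess needs the running totals but not the block size.

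**Patients affected.** An unfinished last block must be allowed for. With 30 patients in blocks of 4 there are seven complete blocks and two patients over. The first two places of a block of 4 are never certain, so the count is 7 × 4/3 = 9.3. With 20 patients in blocks of 6 it is 3 × 1.5 = 4.5, for the same reason.

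| Fixed, known size | Certain, of 30 | Certain, of 20 |
|---|---|---|
| 2 | 15 | 10 |
| 4 | 9.3 | 6.7 |
| 6 | 7.5 | 4.5 |
| 10 | 5.0 | 3.3 |

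**After the change.** Sizes were drawn at random, and the simulated recruiter knew the set of possible sizes and the full history, and updated optimally. Results for 30 patients:

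| Sizes drawn from | Certain, of 30 | Best guess correct |
|---|---|---|
| 4, 6 | 1.76 (6%) | 69% |
| 2, 4, 6 | 1.18 (4%) | 70% |
| 4, 6, 8 | 0.71 (2%) | 67.5% |
| 2, 4 | 3.24 (11%) | 72% |

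For 20 patients the first three rows give 1.1, 0.7 and 0.5 certain assignments, with guess rates of 67–70%. Varying the size therefore removes most of the certain assignments but hardly changes the guess rate. The set 2, 4 does less well than the others.

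**Why blocking is still worth having.** Under simple randomisation of 30, a split worse than 10:20 has probability of about 4%. Some restriction is reasonable; the question is how it is concealed.

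**The case against.** The strongest reply is that much of this rests on silence. Block size, list holder and release mechanism are often recorded outside the protocol, and nothing here says that recruiters hold or see the list. A pre-specified number per block does not strictly exclude sizes that vary from block to block, and leaving the size unprinted is itself consistent with concealment. This stands: the percentages are conditional on a constant size that recruiters know or infer. What remains is that section 3.4 states a balanced-block scheme and provides neither variation nor concealment, in a setting where both matter.

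Visibility is also less than complete. Both arms start with the same home-administered course, and under section 3.6 the monthly pulses begin at Visit 1, at one month. Several physicians recruit, so each would need to know colleagues' assignments in order. At one centre that is plausible but not stated.

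The existing safeguards count too. Randomising after consent prevents a change of mind once the arm is revealed, and a universal offer narrows the room for choice. Neither stops a physician from predicting the next arm before approaching a patient, and the ACTH recommendation that opens the way into the study remains that physician's decision.

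A reader might further infer that section 3.5 contradicts the universal offer, because "we will focus our efforts toward patients with more than one lesion", and that this focus should go. The documents do not support that. Focusing effort on such patients is compatible with offering the study to all. It refers to neither arm and serves a goal of at least 25 lesions in each. By itself it affects who enters the trial, not which arm they enter, and removing it would cost lesions.

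**Conclusion.** The point holds as a design weakness that is cheap to correct. Under a constant block size known to recruiters who also know past assignments, 25–50% of assignments are certain in advance for sizes 2 to 6 (17% at size 10). In patients that is 7.5 to 15 of 30, or 4.5 to 10 of 20. The absence of blinding is inferred from the arms and from the lack of any text on it.

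A reader might infer that the trial's comparison is biased. The documents show only that the opportunity exists. They do not show that anyone foresaw an assignment or acted on it, and they allow no estimate of the size or direction of any bias. Nor should the remedy be read as complete: best-guess accuracy stays near 67–70% with varied sizes, against 50% under unrestricted randomisation.

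**What to change.** In section 3.4:

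- replace the pre-specified block size with randomly varied sizes that are not disclosed to recruiters and not printed in the protocol;
- have the list generated and held by existing institutional staff who do not recruit;
- release each arm only after consent and confirmed eligibility have been recorded.

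This needs a change of wording and a new list, with no extra patients, visits or staff. For the three better size sets above, certain assignments fall to about 2–6%. The set 2, 4 leaves 11%, so the choice of sizes matters. The recruitment focus in section 3.5 can stay.

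The cost is a slightly larger possible imbalance at the end. The difference between arms cannot exceed half the largest block. With sizes up to 8 that is 4 patients, or 17 against 13 of 30, whereas fixed blocks of 2 or 6 would end 30 patients exactly level.

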If patients in either arm have an additional relapse during the study, they will be removed from the study. At that point patients are likely to change on-going treatment for their MS and based upon their treating physician, may require additional steroids (either ACTH or methylprednisolone)

3.3 Inclusion and Exclusion Criteria:

Inclusion criteria:

Patients with RRMS or SPMS with new contrast-enhancing lesions who will start as part of their standard of care ACTH.

Exclusion criteria:

- Patients having received oral or IV corticosteroids within one month prior to initial scan demonstrating contrast enhancing lesion
- Patients with known or new allergy to ACTH
- Patients being treated with Natalizumab, Rituximab, and Cyclophosphamide
- Patients unwilling to have serial MRI exams
- Patients unable to undergo MRI imaging because of having an artificial heart valve, metal plate, pin, or other metallic objects in their body or is unable to complete all the MRI scans required for this study
- Patients with acute or chronic renal disease in whom administration of gadolinium may pose risk of nephrogenic systemic fibrosis
- Patients that are pregnant
- Premenopausal woman not willing to use at least one form of contraception
- Patients with a known history of diabetes mellitus
- Progressive neurological disorder other than RRMS or SPMS
- Clinically significant cardiovascular disease, including myocardial infarct within last 6 months, unstable ischemic heart disease, congestive heart failure, or angina
- Subjects on chronic steroid therapy for treatment of MS or other systematic disease
- Subject currently has a significant medical condition (other than MS) including the following: neurological, psychiatric, metabolic, hepatic, renal, hematological, pulmonary, cardiovascular (including uncontrolled hypertension), gastrointestinal, urological disorder, or central nervous system (CNS) infection that would pose a risk to the subject if they were to participate in the study or that might confound the results of the study
 - Note: Active medical conditions that are minor or well-controlled are not exclusionary if, in the judgment of the Primary Investigator, they do not affect risk or the subject or the study results.

- Subject is unable to cooperate with any study procedures, unlikely to adhere to the study procedures and keep appointments, in the opinion of the Investigator, or was planning to relocate during the study

3.4 Randomization procedure:

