Baseline visit: Baseline EDSS (if not obtained during screening visit), *consent signed*, schedule repeat MRI with and without contrast if screening MRI not completed as part of the Weill Cornell Multiple Sclerosis Center Clinical Protocol. Initiation of ACTH (H.P. Acthar®) course of therapy following visit (patient will do home therapy) after randomization.

Visit 1: EDSS, safety evaluations, and initiation of monthly course of ACTH (H.P. Acthar®) in patients randomized to this arm.

Visit 2: EDSS, safety evaluations.

Visits 3, 4, 5: EDSS, safety evaluations, MRI with and without contrast

Visit 6 (last visit): EDSS, safety evaluations, MRI with and without contrast.

3.7 Study schema:

Tests and Evaluations	Time point: screening/ Baseline	Visit 1 (1 month)	Visit 2 (2 months)	Visit 3 (3 months)	Visit 4 (6 months)	Visit 5 (9 months)	Visit 6 (12 months- end of study)
Consent obtained	X						
MS history and EDSS, safety evaluations	X	X	X	X	X	X	X
Randomization to treatment arm	X						
MRI	X			X	X	X	X

4 Assessment and documentation of adverse events

An AE is any physical or clinical worsening in symptoms or disease experienced by the patient at any time during the course of the study, whether or not it is considered related to study participation

or procedures. Multiple sclerosis symptoms that worsen during the course of the trial will be treated as AEs. AEs may also include complications that occur as a result of protocol-mandated procedures.

ACTH Safety Background

ACTH has been approved by the US Food and Drug Administration for treatment of MS relapses, however, we are proposing to use this drug on a monthly pulsed dosing (80mg for three days per month) schedule for one year. A few trials have evaluated the longer-term clinical benefit and safety profile of ACTH pulse therapy in idiopathic glomerular diseases, such as nephrotic syndrome and focal segmental glomerulosclerosis (FSGS), as well as one pilot study in MS. These studies had varying dosing schedules, some of which included a higher per month drug exposure as compared to our proposed study [26-30]. None of the studies reported severe-events related to ACTH and the adverse events were consistent with the expected common side effect profile listed on approved label. Based upon these studies, the adverse events between the two groups of patients proposed in this study should be similar.

The studies are summarized below.

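### For patients whose lesion was found on a scan outside the centre's protocol, nothing requires the baseline MWF scan to precede the first ACTH dose, and a short steroid course between the two scans is not excluded

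*Protocol*

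**What the plan says.** Protocol 3.1 describes two routes to a baseline scan. A patient whose enhancing lesion was seen on a scan done at the centre under its own protocol keeps that scan. For a lesion found on a scan from elsewhere, "an additional scan will be obtained through the study and serve as the baseline MRI".

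Protocol 3.6 (Baseline visit) says when this second scan is arranged: "schedule repeat MRI with and without contrast if screening MRI not completed" under the centre's clinical protocol. The same entry has ACTH begin as a "course of therapy following visit (patient will do home therapy) after randomization".

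The limit on when ACTH starts is in 3.1: "All patients will receive the first course of ACTH within 4 weeks of new lesion detection". Section 3.6 (Screening visits) adds a recency condition for the detecting scan: "If a patient had MRI within 2 weeks of visit and had new enhancing lesions".

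On earlier steroids, 3.3 excludes "Patients having received oral or IV corticosteroids within one month prior to initial scan demonstrating contrast enhancing lesion" and, separately, "Subjects on chronic steroid therapy for treatment of MS or other systematic disease".

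Under 3.2, the primary endpoint is the absolute change in lesion MWF from the baseline scan to the one-year scan, compared between arms.

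**The concern.** For patients who need a repeat scan, the start of ACTH depends on randomisation, and randomisation depends on signed consent (3.4). Neither depends on the repeat scan being done. A site could dose first and scan afterwards without breaking any written rule. The steroid exclusion has a matching gap: for these patients the detecting scan is not the baseline scan, so the interval between the two is unprotected.

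This matters because of what the protocol says about its own measure. Section 1.2 states that MWF responds to edema and that ACTH is anti-inflammatory. A lesion first measured during or after treatment may already have lost part of its edema. The extracellular-peak adjustment uses the change in that peak over time, so movement before the baseline scan is invisible to it. The secondary aim, the timing of remyelination, is exposed too, since its time zero would differ between patients. No later analysis can recover a pre-treatment scan that was never taken.

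**Working it through.** The plan gives no figure for this point, so the check is mainly one of sequence.

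**1. Timeline for a patient who needs a repeat scan**

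| Event | Limit in the protocol | Source |
|---|---|---|
| Lesion detected | day 0 | 3.1 |
| Screening visit | within 14 days of the detecting scan | 3.6 |
| First ACTH dose | by day 28 | 3.1 |
| Repeat (baseline) scan | scheduled at the baseline visit; no date limit and no order relative to ACTH | 3.6 |

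The schema in 3.7 does not settle the order. Consent, randomisation and MRI share one screening/baseline column.

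**2. How much treatment could precede the scan.** Section 3.1 expects 3-5 days of initial ACTH for most patients and allows up to 2-3 weeks. The number of dose days before the scan is min(delay from first dose, course length):

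- Delay of 3 days: 3 of 3, or 3 of 5.
- Delay of 5 days: 3 of 3, or 5 of 5.
- Delay of 7 days: the whole of a 3- or 5-day course, and 7 days of a 21-day course.

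An ordinary wait of a week for a scan is therefore enough to put the baseline after the whole typical course.

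**3. Steroid gap.** The first exclusion in 3.3 looks back one month from the detecting scan. The second covers chronic therapy only. A short course given after the detecting scan and before the repeat scan meets neither.

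**4. Illustrative size.** Let f be the share of patients with a post-treatment baseline and e the early MWF shift that this baseline misses. The documents give neither. Assume f = 10-50% and e = 0.02-0.045; the upper value borrows the pilot's threshold for true change in 1.2. The patient is the unit.

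- Shift in mean 12-month change, f × e: 0.10 × 0.02 = 0.002, up to 0.50 × 0.045 = 0.0225.
- Added SD, e × √(f(1−f)): 0.02 × √0.09 = 0.006, up to 0.045 × √0.25 = 0.0225.
- SE of the arm difference from chance imbalance, 15 per arm, e × √(2f(1−f)/15): 0.02 × √(0.18/15) = 0.0022, up to 0.045 × √(0.50/15) = 0.0082.
- Section 3.5 counts about 10 screen failures within the 30. With 10 per arm (30 − 10 = 20, divided by 2), the SE is 0.02 × √(0.18/10) = 0.0027, up to 0.045 × √(0.50/10) = 0.0101.

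These are sizes only. The sign is left open because 1.2 says MWF can rise with edema, while its first lesion example links an MWF gain to an edematous lesion that was resolving.

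**The case against.** The natural reading puts the scan first. Section 3.6 lists consent, then the repeat scan, then ACTH; 3.7 places the scan in the baseline column; and 3.1 calls it the baseline. Nothing directs a post-dose baseline. This stands as far as it goes: the defect is an unstated order, not a contradiction, and it does not show that treated baselines occurred.

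A reader might infer that the protocol permits corticosteroids in the gap. It does not say so; it only fails to exclude them. Entry requires that ACTH be the planned standard-of-care treatment (3.3), so a steroid course just beforehand is probably unusual.

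A reader might also infer bias between arms, for example through different scanning delays once allocation is known. The documents do not support this. Both arms receive the same initial course, and monthly pulses start only at Visit 1, a month later. No reason is given why the arms would be scanned at different times.

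The 137% MWF gain of the edematous lesion in 1.2 is a tempting measure of the damage. It is one lesion's longitudinal change, attributed to edema only in part, and not the shift over a few days of ACTH.

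Finally, the protocol does have edema controls: the extracellular peak and the exploratory absolute myelin content. They reduce the problem but do not remove it, because the peak adjustment itself starts from the baseline scan. Recruitment from the centre's own database also suggests that repeat scans may be the exception, though no share is stated.

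**Conclusion.** The point holds for the subset of patients who need a repeat scan. As written, their primary-endpoint baseline can fall during or after the initial ACTH course, or after a short steroid course. The expected harm is a mixture of untreated and treated baselines, with added noise, distorted within-arm change and a blurred time zero for the timing aim. Systematic bias in the arm comparison is not shown; chance imbalance in a sample this small remains possible.

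The size cannot be fixed from the documents. Under the assumed ranges it runs from negligible (0.002) to half of the pilot's 0.045 threshold (0.0225 / 0.045 = 0.5). The upper end requires both that half the patients are affected and that the early shift is as large as the threshold itself. The point is worth correcting because it touches the primary measurement, cannot be repaired in analysis and is cheap to close.

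**What to change.** Reconcile 3.1, 3.3 and 3.6 as follows.

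- **3.6:** state that a patient is randomised only once the study baseline MWF scan is complete and before any dose of the initial ACTH course has been given. A patient who cannot be scanned in time is treated as standard of care and is not randomised. This is a condition for randomisation, not a delay of relapse treatment, and it matches what 3.1 already provides for patients who do not enrol.
- **3.3:** tie the corticosteroid exclusion to the scan that serves as the baseline as well as to the initial detecting scan.
- **Data collection:** record the dates of the detecting scan, the baseline scan and the first ACTH dose, so that the order can be verified and reported.

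The cost is a few sentences of protocol text, tighter scan scheduling, and possibly a few patients lost to eligibility in a study that is already small. No dose or treatment rule changes.

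### Randomisation at baseline comes before an adjustable initial ACTH course meant to be common to both arms, so the arm can be known while that course is set; randomising at Visit 1 would prevent this

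*Protocol*

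**What the plan says.** **Order of events.** Section 3.4 states: "Patients will be randomized after the consent is signed". Section 3.6 places consent at the baseline visit and starts the initial ACTH "course of therapy following visit (patient will do home therapy) after randomization". The schema in section 3.7 also marks randomisation at screening/baseline.

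**A shared first stage.** Section 3.1 says: "The initial stage of the study is for all patients to receive the standard of care course of ACTH". Only the later monthly doses depend on the arm. In section 3.6, Visit 1 (month 1) is the point of "initiation of monthly course of ACTH (H.P. Acthar®) in patients randomized to this arm".

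**Room to adjust.** Section 3.1 expects most patients to start at 80 units/day for 3-5 days. It also says that "the frequency and dose of the drug may be determined by considering the severity of the disease and the initial response of the patient". The descriptions of both groups carry the same allowance: "The dose could be adjusted based on the individual needs of the patients up to 80-120 units daily for 2-3 weeks".

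**Contrast and endpoint.** Group B's initial course is "followed by monthly 80 units/day ACTH for 3 days for 12 months of treatment"; Group A has the one course only. No placebo pulses and no masking of patient or physician are described. The primary endpoint (section 3.2) is lesion MWF change between the baseline and one-year scans.

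**The concern.** Specific aim 1 asks whether monthly pulses add to a single course. A clean answer needs the single course to be the same in both arms, apart from chance. Here the course is chosen and adjusted after allocation, partly on a response that can only be seen after allocation, by physicians who have no stated reason not to know the arm. A physician who knows that no pulses will follow might extend the first course; one who knows that pulses will follow might keep it short.

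The endpoint runs from baseline, so it includes whatever the initial course does. Section 3.5 itself links remyelination to this period: it reports that at least half of new enhancing lesions show some repair after initial acute treatment. A difference in initial treatment caused by knowledge of the arm would be counted with the effect of the pulses, and the month-12 comparison could not separate them.

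**Working it through.** The protocol gives no figure to reproduce here. The check is of sequence, followed by simple dose arithmetic.

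**Sequence**
1. Consent and randomisation: baseline (3.4, 3.6, 3.7).
2. Initial course: after randomisation, adjustable in both groups (3.1, 3.6).
3. First planned difference between arms: Visit 1, month 1 (3.6).
4. Endpoint interval: baseline to month 12 (3.2), so step 2 lies inside it.

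Nothing fixes the initial regimen before step 1 or withholds the allocation until step 3. The longest initial course is 21 days, so if started promptly it is over by Visit 1.

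**Permitted initial exposure** (units/day x days, from 3.1)
- Expected for most patients: 80 x 3 = 240 to 80 x 5 = 400 units.
- Extended course: 80 x 14 = 1,120 to 120 x 21 = 2,520 units.
- Spread between individual extremes: 2,520 - 240 = 2,280 units.

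**Planned extra exposure in Group B**
- Each pulse: 80 x 3 = 240 units.
- Twelve pulses: 240 x 12 = 2,880 units. If only eleven fit between month 1 and the end (an assumption): 240 x 11 = 2,640 units.
- Spread relative to this: 2,280/2,880 = 79%; 2,280/2,640 = 86%. This compares one patient's possible extremes with a between-arm difference, so it shows latitude and does not estimate bias.

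**Illustration of a shift in an arm mean** (assumption; the documents give no distribution of initial courses). Suppose k of the 15 Group A patients go from 320 units (80 x 4) to 1,120 units because no pulses will follow. The Group A mean rises by (k/15) x (1,120 - 320) = (k/15) x 800.
- k = 1: 53 units, or 1.9% of 2,880 and 2.0% of 2,640.
- k = 3: 160 units, or 5.6% and 6.1%.
- k = 5: 267 units, or 9.3% and 10.1%.

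The protocol gives no relation between units of ACTH and MWF, so none of these figures converts into bias in the endpoint.

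**Direction.** If ACTH aids remyelination, extra initial treatment in Group A narrows the difference between arms; extra in Group B would widen it.

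**The case against.** The strongest reply is that this is a conventional order, stated consistently in every place. The protocol says when patients are randomised, not when the prescriber learns the arm; open-label is an inference from the lack of placebo and masking. The treating physician recommends ACTH before the study is offered. The grounds for adjustment are clinical and the same in both arms, and the arm is not among them. Most patients are expected to receive the short course. The trial is a small pilot meant to inform a larger one.

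Much of this stands. There is no contradiction in the text, and nothing shows that physicians would treat the arms differently. But recommending ACTH beforehand settles the drug and leaves its dose and duration open. Equal permission does not give equal use when the arm is known. The expectation of a short course is not a limit. With 15 patients per arm, a few departures move a mean. A pilot meant to guide a larger trial needs an unblurred contrast as well.

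Two stronger readings are tempting, and the documents support neither:
- **That the bias could rival the treatment contrast,** because the top of the initial range (2,520 units) is close to the pulse total. This would need nearly all of Group A at one extreme and all of Group B at the other. Cumulative units are also a doubtful yardstick, since the hypothesis concerns continued monthly exposure rather than total dose.
- **That losses in month 1 add to the bias,** because section 3.2 removes patients who relapse. Each loss is 1/15 = 6.7% of an arm, but planned treatment does not yet differ and no arm-related mechanism is given. Such losses mainly cost precision, and no month-1 loss rate is stated.

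**Conclusion.** The point holds as a design weakness with an inexpensive remedy. A treatment meant to be common to both arms is set and adjusted after randomisation, when the arm can be known, and it falls inside the interval of the primary endpoint. This opens a route to bias; it does not show that bias will occur. A reader might infer that the arms will in fact receive different initial courses, or that the result is bound to favour the pulses. The protocol supports neither, and the scenario that comes most readily to mind, longer courses in Group A, would dilute a true benefit.

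Neither the size nor the direction of any bias can be computed. The conclusion rests on two assumptions: that allocation is in practice known to patient and physician, inferred from the absence of placebo and masking, and that initial exposure can affect MWF, which is the protocol's own premise.

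**What to change.** Keep consent, the baseline MRI and the initial course as they are. Move randomisation, or at least the opening of the allocation, to Visit 1, immediately before the first pulse would start. This means rewording sections 3.1, 3.4 and 3.6 and moving one mark in the section 3.7 schema. It needs no extra visit, procedure or patient, and the permuted blocks work as before.

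The cost is that patients learn their arm a month later and, if randomisation itself moves, those who relapse or leave in month 1 are not randomised. The conclusion then applies to patients who complete the initial course, and the protocol should say so.

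If randomisation stays at baseline with the allocation open, record the intended initial dose and duration before it is opened, and report actual initial exposure by arm. This protects only in part, because changes made on early response would still follow allocation. No dose or clinical rule is proposed in either case.
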